#### 7.4.2 Reporting of Serious Adverse Events, Including Death

The Sponsor will adhere to all expedited regulatory reporting requirements as per 21 CFR 312.32.

If an SAE, including death occurs during this study or within 30 days following the last dose of the study treatment, the Investigator must notify the Medical Monitor **within 24 hours** after becoming aware of the event.

Initial notification via the telephone does not replace the need for the Investigator to complete and sign the SAE form within the time frames outlined in the protocol. This timeframe also applies to additional new information (follow-up) on previously forwarded SAE reports. The contact information for the Medical Monitor is provided below.

##### **Medical Monitor:**

[name]  
Safety Office, Integrium, LLC  
Office: [contact]  
Cellular: [contact]  
Email: [[contact]](mailto:[contact])

SAE Forms will be provided by the Sponsor or Sponsor designated contract research organization (CRO). If all information is not known at the time of initial reporting, an initial report should still be made. In the event there is a question as to whether the experience is serious, the information should be forwarded to the Medical Monitor for review. The Investigator is responsible for following up on completion of the SAE Form. For all serious adverse events, the Investigator must pursue and provide information to the Study Medical Monitor in accordance with the timeframes for reporting specified above. In general, this will include a description of the adverse event in enough detail to allow for a complete medical assessment of the case and independent determination of possible causality. Information on other possible causes of the event, such as concomitant medications and illnesses, must be provided. In the case of a subject death, a summary of available autopsy findings must be submitted as soon as possible to the Medical Monitor”.

In the event of a medical emergency or an SAE that is unexpected (as defined in [Section 7.8](#)) and possibly related to the study treatment (s) (i.e., an adverse reaction or suspected adverse reaction as defined in [Section 7.6](#)), in the opinion of either the Investigator or the Medical Monitor, the blind will be broken for the subject that experiences the event. If the Investigational Site personnel need to unblind the study treatment they can contact the unblinded programmer and pharmacist.

The initial SAE Form and any subsequent follow-up SAE Forms submitted to provide more accurate, corrected, or new information must be signed by the Investigator. The Investigator and

Investigational Site Personnel must make every reasonable effort to obtain, from other institutions if necessary, all supporting medical case records as needed to comply with expedited Investigational New Drug application (IND) safety reporting requirements.

If the SAE involves expedited IND safety reporting (as determined by the Sponsor or designee), all supporting medical records must be submitted to the Sponsor or designee within 4 calendar days for death or life-threatening events, and 10 calendar days for all other events. In cases where medical records and supporting documentation are unobtainable, the Investigator must generate a narrative of the event utilizing, when necessary, interviews with the subject, their family members and care givers as appropriate.

The Investigator must also promptly inform the governing IRB of the SAE in accordance with the governing IRB's requirements. Any SAE that is determined by the Sponsor to be reportable to the FDA as an IND Safety Report (as defined in 21 CFR 312.32) will be reported to FDA by the Sponsor or designee within the specified time frame. All IND Safety Reports will also be promptly provided to the Investigator for submission to his/her IRB. Similarly, any SAE that is determined by the Sponsor to require expedited reporting to other regulatory authorities will be reported to the appropriate authorities by the Sponsor or designee within the specified time frames, and will be provided to the Investigator for submission to his/her IRB.

The Investigator, Medical Monitor, and Sponsor will review each SAE report and evaluate the relationship of the adverse experience to study treatment and to underlying disease. Based on this assessment, a decision will be made concerning the need for further action. The primary consideration governing further action is whether new findings affect the safety of subjects participating in the clinical trial. If the discovery of a new adverse experience related to the study treatment raises concern over the safety of continued administration of study treatment, the Sponsor will take immediate steps to notify the regulatory authorities.

Further action that may be required includes the following:

1. Alteration of existing research by modification of the protocol;
2. Discontinuation or suspension of the study;
3. Alteration of the informed consent process by modification of the existing consent form and informing current study participants of new findings;
4. Modification of previously identified expected adverse experiences to include adverse experiences newly identified as study treatment-related.

#### 7.4.2.1      Pregnancy Reporting

If the subject or partner of a subject participating in the study becomes pregnant during the study or within 30 days of discontinuing study medication, the Investigator should report the pregnancy to Integrium within 24 hours of being notified. Safety personnel will then forward the Exposure In Utero form to the Investigator for completion.

The subject or partner should be followed by the Investigator until completion of the pregnancy. If the pregnancy ends for any reason before the anticipated date, the Investigator should notify the Sponsor. At the completion of the pregnancy, the Investigator will document the outcome of the pregnancy. If the outcome of the pregnancy meets the criteria for immediate classification as an

SAE (i.e., postpartum complication, spontaneous abortion, stillbirth, neonatal death, or congenital anomaly), the Investigator should follow the procedures for reporting an SAE.

#### 7.4.3 Adverse Events of Hypoglycemia

Hypoglycemia and associated symptoms (e.g., weakness, dizziness, shakiness, increased sweating, palpitations, or confusion), have been associated with insulin administration, including ORMD-0801. Animal reproductive studies have not been conducted with ORMD-0801. It is not known whether ORMD-0801 can cause fetal harm when administered to a pregnant woman. It is also not known whether this product is excreted in human milk. Pregnant or breastfeeding women are excluded from this study.

Long-term animal studies have not been completed to assess whether ORMD-0801 impairs fertility.

Due to the specific relevance of hypoglycemia as a limiting factor in insulin therapy, AEs of hypoglycemia will be reviewed at every visit. All hypoglycemic events will be reported on a special hypoglycemia AE eCRF page. This will include the following information:

- Subject symptoms;
- Type of symptoms;
- BG value during the hypoglycemic event and the event severity based on CTCAE criteria;
- Whether treatment was required;
- Whether assistance was required for treatment;
- What specific treatment, if any, was used.

Instructions will be given to sites to additionally report episodes consistent with hypoglycemia requiring third party assistance as Serious Adverse Events (SAE).

Collection of data from the hypoglycemia AE eCRF including episodes consistent with hypoglycemia will allow analysis and characterization of hypoglycemia according to accepted ADA definitions (Sequist et al, 2013) and according to common cut-off values, such as BG < 70 mg/dL and < 53 mg/dL for example.

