## 1 INTRODUCTION

Endogenous insulin – secreted by the  $\beta$ -cells of the endocrine pancreas – flows to the liver in the portal blood before reaching the systemic circulation through the hepatic veins. Following oral administration, the insulin in ORMD-0801 is absorbed through the gastrointestinal mucosa into the mesenteric veins (mostly, the superior mesenteric vein that drains blood from the jejunum and ileum) and reaches the liver *via* the portal vein, thereby mimicking the route of entry of endogenous insulin. The main action of insulin in the liver is to suppress glucose production; for this action, sensitivity is higher, and onset and offset time of this action are faster than for insulin stimulation of glucose uptake by peripheral tissues. First-pass extraction of insulin by the liver is 50-60%; recirculation raises this percentage to ~80%. As a consequence, portal plasma insulin concentrations normally are ~3-fold higher than peripheral insulin levels.

The hypothesis behind ORMD-0801 is that sufficient oral insulin survives gastrointestinal degradation to arrive at the liver where it inhibits glucose production and, through this effect, lowers fasting plasma glucose concentrations. As the majority of this exogenous insulin dose is degraded in the liver, the resulting systemic insulin levels may be only marginally increased, thereby avoiding the risk of hypoglycemia.

The use of glucose tracers is the standard non-invasive approach to measure endogenous glucose production (EGP). A tracer (in this protocol, [6,6-H2]-glucose, a stable isotope of glucose) infused intravenously at a constant rate will equilibrate with endogenous glucose across its distribution space within ~3 hours. From this time onward, the ratio of the tracer infusion rate to the plasma tracer/tracee ratio (as assayed by GCMS) measures EGP. As compared to placebo, oral insulin is expected to reduce EGP over the ensuing 13 hours of continued fasting. In patients with type 2 diabetes, EGP is known to be abnormally elevated and to contribute the hyperglycemia. Oral insulin is therefore addressing a key pathophysiological derangement of type 2 diabetes.

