
### 3 INVESTIGATIONAL PLAN

#### 3.1 Overall Study Design and Plan

This study is designed to explore the efficacy of ORMD-0801 compared to placebo on endogenous glucose production in subjects with type 2 diabetes (T2DM). Subjects will undergo an initial Screening Visit (Visit 0) to establish their eligibility to participate in the study. At Visit 1 (2 weeks after the Screening Visit), qualifying subjects will be randomized to either ORMD-0801 (8 mg) or matching placebo, study medication will be dispensed and subjects will dose, twice a day, once in the morning prior to breakfast and once at night prior to bedtime. Doses will occur at 45 minutes ( $\pm$  15 minutes) before breakfast and no later than 10 AM each morning, and at 8 PM ( $\pm$  120 minutes) each night, and no sooner than 1 hour after dinner. Subjects will return to the clinic, 2 weeks later, for Visit 2. At this visit, subject compliance will be assessed, medication will be dispensed, a blood sample will be collected to measure HbA1c and subjects will be questioned for any adverse events. Subjects will be scheduled to return to the clinic in 2 weeks for morning admission (8 AM  $\pm$  120 minutes) to the PK unit (Visit 3). Subjects will be provided with standardized meals and the morning dose in-clinic. A light standardized dinner meal will be provided at 6 PM  $\pm$  30 minutes. At approximately 8 PM ( $\pm$  60 minutes, and no sooner than 1 hour after dinner), subjects will be dosed with their study medication and will be started on a 16-hour infusion of [6,6-H2]-glucose tracer. Blood samples will be collected to measure endogenous glucose (tracer attached), plasma glucose, metabolites and hormones for the duration of the infusion. Blood samples will be drawn at baseline (pre-infusion), 45, 90, 120 and 150 minutes, and 3, 4, 5, 6, 7, 8, 9, 10, 11, 12, 13, 14, 15 and 16 hours (see [Table 2](#) for blood draw schedule). Subjects will be required to remain fasting from the evening of Day 28 until the end of the infusion. Water intake will be unrestricted. On Day 29, blood sample will also be collected to measure HbA1c. Following completion of the infusion, the subjects will receive a standardized lunch and will be observed for an additional 6 hours. Prior to discharge, a physical examination will be performed, and blood/urine samples will be collected for safety chemistry, hematology and urinalysis, following which subjects will be discharged from the CRU and will exit the study.

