#### 6.1.5 Clinical Laboratory Tests

Fasted blood and urine samples for clinical safety laboratory assessments will be collected and processed using standard procedures as indicated in [Table 1](#). Laboratory samples will be processed by appropriate laboratories.

In the event of abnormal clinical laboratory values, the Investigator will make a judgment whether or not the abnormality is clinically significant.

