### 6.2.3 Plasma Glucose Levels

Plasma glucose levels will be collected prior to dosing and after 28 days of dosing. The plasma glucose levels collected after the 16-hour infusion period is complete is the value that will be analyzed for this test.

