### 7.2 Definition of Adverse Event

An adverse event (AE) is defined in 21 CFR 312.32(a) as follows:

Any untoward medical occurrence associated with the use of a drug in humans, whether or not considered drug related.

An AE can be any unfavorable and unintended sign (e.g., an abnormal laboratory finding), symptom, or disease during the course of the study, and does not imply any judgment about causality.

Treatment-emergent adverse events (TEAEs) are defined as any AE that starts or increases in severity after the first randomized dose of study treatment (active or placebo).

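### The plan does not say whether timed infusion plasma glucose values below 70 or 53 mg/dL count as hypoglycemia, so rates taken from the AE page may miss asymptomatic lows

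*Combined protocol and SAP*

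**What the plan says.** **Hypoglycemia.** Secondary endpoint 7 (Section 2) assesses safety through AE reporting and singles out hypoglycemia. Section 7.4.3 sets the route: "All hypoglycemic events will be reported on a special hypoglycemia AE eCRF page". The page records symptoms, the glucose value, severity, treatment and assistance. The section then states the analytic purpose: "Collection of data from the hypoglycemia AE eCRF including episodes consistent with hypoglycemia will allow analysis and characterization of hypoglycemia", by ADA definitions and by "common cut-off values, such as BG < 70 mg/dL and < 53 mg/dL for example".

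**Timed glucose.** Section 3.1 says: "Blood samples will be collected to measure endogenous glucose (tracer attached), plasma glucose, metabolites and hormones for the duration of the infusion". Table 2 gives plasma glucose its own column at every draw. The only named analysis of plasma glucose is the change-from-baseline comparison, and Section 6.2.3 limits it: "The plasma glucose levels collected after the 16-hour infusion period is complete is the value that will be analyzed for this test". Section 8.4.3 says the same.

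**How a low value could become an AE.** Section 7.2 says: "An AE can be any unfavorable and unintended sign (e.g., an abnormal laboratory finding), symptom, or disease". Section 7.4 requires documentation of AEs that site staff observe or identify, as well as those that subjects report. For abnormal safety laboratory values, Section 6.1.5 says: "the Investigator will make a judgment whether or not the abnormality is clinically significant".

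**General provisions.** Section 8.5.8 promises descriptive statistics and listings for all data. The opening of Section 8 leaves further detail to a statistical analysis plan; the supplied document contains no separate SAP text.

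**The concern.** The infusion night is the trial's only dense, objective glucose record taken at the same times in both arms. It follows an evening dose and runs through a long fast, and subjects will presumably be asleep for part of it. A low value without symptoms in that window becomes part of the hypoglycemia rate only if someone at the site recognises it and enters it on the AE page.

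Two features of the protocol sharpen this. Section 7.4.4 defines hyperglycemia by a number, above 300 mg/dL whatever the symptoms, whereas Section 7.4.3 sets no number at which a low reading becomes an event. Its cut-offs are examples, applied to data already on the page. Exclusion criterion 5 also recognises that documented low glucose can occur without autonomic symptoms.

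At stake is how complete a named safety endpoint is. The Introduction expects that systemic insulin may rise only marginally, "thereby avoiding the risk of hypoglycemia". A missed low can only reduce the recorded rate, which is the direction of that hypothesis.

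**Working it through.** **Step 1. Count the samples (Table 2, Section 3.1).**
- Baseline, 45, 90, 120 and 150 minutes: 5 draws. Hourly from 3 to 16 hours: 14 draws. Total 5 + 14 = 19.
- Check against Table 2: 19 × 1 mL = 19 mL in the glucose column. All tubes: 19 × 9 mL + 2 × 4 mL backup = 179 mL. Both totals are reproduced.
- One draw is before the infusion and 18 are during it or at its end. With the 20:00 start in Appendix A, the 18 run from 20:45 to 12:00, so the last few are morning samples.
- With about 40 subjects (Section 5.2): 19 × 40 = 760 values, of which 18 × 40 = 720 come after the infusion starts. These counts show how much information exists; they do not measure missed events.

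**Step 2. See whether any named analysis sets the serial values against a cut-off.**

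| Section | What it covers | Serial plasma glucose? | Cut-off count? |
|---|---|---|---|
| 7.4.3 | Hypoglycemia AE page | Only if entered as an event | Yes, on page data |
| 6.2.1, 8.4.1 | Endogenous glucose production, metabolites, hormones | Not listed | No |
| 6.2.3, 8.4.3 | Plasma glucose after the infusion | End value only | No |
| 8.5.2 | TEAE incidence | Only if entered as an AE | No |
| 8.5.3 | Hematology, serum chemistry, urinalysis | No | No |
| 8.5.8 | All data, listings and descriptive statistics | Yes | No |

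No row turns a Table 2 value below 70 or 53 mg/dL into a counted event without a prior decision at the site. Section 9.1.1 sends laboratory results to the CRO for import into the database and does not mention prompt return to the investigator.

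**Step 3. Illustrate what incomplete capture could do.** The documents give none of the following inputs; all are assumptions:
- n = 20 per arm (the allocation ratio is not stated);
- p = share of subjects in an arm with at least one low timed sample;
- s = probability that such a subject's low reaches the AE page, independently between subjects.

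Counting lows from the timed samples only, the chance of no recorded event in the arm is (1 − p·s)^20.

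| p | s = 1 | s = 0.5 | s = 0.25 |
|---|---|---|---|
| 5% | 0.95^20 = 36% | 0.975^20 = 60% | 0.9875^20 = 78% |
| 10% | 0.90^20 = 12% | 0.95^20 = 36% | 0.975^20 = 60% |
| 20% | 0.80^20 = 1% | 0.90^20 = 12% | 0.95^20 = 36% |

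**Step 4. What a zero count would mean.** For 0 of 20, the one-sided 95% upper bound is 1 − 0.05^(1/20) = 13.9%. That bound still covers an assumed true rate of 10%, and even full capture gives zero events with probability 12% at that rate.

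**The case against.** A reader might infer that the plan excludes the timed samples, that lows in them go uncounted, and that the drug will therefore look free of hypoglycemia. The documents do not support this. Section 7.4.3 says that the page data will allow the analysis; it does not bar other sources. Reporting of hypoglycemic events is mandatory, an abnormal laboratory finding can be an AE, Section 7.4 covers events that staff identify, and the page records symptoms separately from the glucose value. A symptom-free low therefore has a route to being counted. These points stand, and they make the matter a gap in specification rather than an exclusion.

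Nor are the values hidden. Section 8.5.8 promises them in listings and descriptive statistics. If the range is among those statistics, as in Sections 8.5.3 and 8.5.4, a low would show as a minimum at its time point. This stands too, but a listing or a minimum is not a count of affected subjects by arm, and a mean can conceal an individual low.

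Endpoint 7 is defined through AE reporting, so the AE page matches the endpoint, and the SAP may already contain a cut-off table. Both points are fair. The proposal supplements the endpoint and leaves its definition alone, and the SAP would be a proper home for it.

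Finally, both arms are blinded and follow the same reporting rules. That guards against unequal capture but not against incomplete capture: if s is the same in both arms, a true difference in rates is recorded as s times that difference.

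**Conclusion.** The point holds as a gap. The AE page is the only stated source for the cut-off characterization. No rule or table counts a Table 2 plasma glucose value below 70 or 53 mg/dL as hypoglycemia, and no numeric trigger requires one to be reported. Rates from the page depend on site recognition and judgment and may miss asymptomatic lows during the infusion.

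The size of any undercount cannot be derived, because the documents give neither the frequency of lows nor the share that would be reported. On the assumptions of 20 per arm and 10% with a low sample, the chance of zero recorded events rises from 12% with full capture to 36% at half and 60% at a quarter. A reader might go further and call a reported 0 of 20 wrong rather than imprecise. The 13.9% bound does not support that, since it covers the assumed 10%. With entry HbA1c of 7.5% to 11%, lows may also be few.

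The change is worth making because it replaces discretionary capture with an objective count from data already collected. Neither the primary endpoint nor the validity of the trial depends on it.

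**What to change.** In Sections 7.4.3 and 8.5, or in the SAP to which Section 8 refers, state that hypoglycemia by cut-off will also be derived by program from every Table 2 plasma glucose value. Add one table giving, by arm:

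- the number and percentage of subjects with any value < 70 mg/dL and with any value < 53 mg/dL;
- the number of samples below each cut-off;
- the lowest value over 0–16 hours, with the pre-infusion sample shown separately;
- AE-reported hypoglycemia alongside, with the lows split by whether symptoms were recorded.

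Fix this before unblinding, so that the count is not chosen after the results are known.

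The cost is some wording and one extra table, with no additional blood, visits or assays. The reported hypoglycemia rate may become less favourable; if there are no lows, the table supports the sponsor's hypothesis better than AE reports alone. The change concerns only how values are counted and proposes nothing about clinical management.

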#### 7.4.4 Adverse Events of Hyperglycemia

Hyperglycemia is the result of inadequate treatment and a pre-condition for enrolment into the study, therefore in general hyperglycemia is not considered an AE. However, hyperglycemia may occur in participants during the study either due to worsening diabetes or lack of efficacy of study medication. For standardization purposes, hyperglycemia is defined as a blood glucose reading > 300 mg/dL regardless of symptoms. Subjects who have a blood glucose reading > 300 mg/dL will have the reading repeated 1-2 hours later. If a subject's glucose remains above 300 mg/dL or for persistent symptoms of hyperglycemia, the subject will be instructed to contact the investigative site for follow-up.

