#### **3.3.2 Visit 2 (Week 2, Day 14)**

Subjects will report to the clinic in morning following a 10-hour fast. At Visit 2, the following procedures will be performed:

- Review of prior and current medications and supplements;
- Measurement of vital signs (SBP/DBP and heart rate);
- Measurement of weight;
- Breathalyzer;
- Study medication will be collected, and compliance will be reviewed;
- Study medication will be dispensed;
- Blood sample will be collected to measure HbA1c;
- AEs/SAEs assessment;
- Remind subjects to arrive fasting for Visit 3 in 2 weeks.

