### **3.6 Early Withdrawal (EW)**

If a randomized subject is withdrawn from the study prior to completion, the subject will be instructed to return to the clinic the next day and will have the early term (ET) visit procedures completed. Subjects will then be discharged from the study. Subjects will report to the clinic in morning following a 10-hour fast. Subjects will complete the following evaluations:

- Review of prior and current medications and supplements;
- Physical examination;
- Measurement of weight;
- Measurement of vital signs (SBP/DBP and heart rate);
- Collection of fasted blood and urine samples for clinical safety labs for hematology, serum chemistry and urinalysis (see [Section 6.1.5.1](#) for list of tests);
- AEs/SAEs assessment;
- Discharge from CRU, if applicable.

Any subject with a possible study treatment related AE at the time of EW will be followed until resolution or stabilization of the event.

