**Table 1: Schedule of Events from Screening (Visit 0) to Discharge/End of Study (Visit 3, Day 29).**

	Screening	Treatment Period			Discharge / End of Study	Early Withdrawal
				TRACER Infusion		
Visit	0	1	2	3		
Week	-3 to -1	0	2		4	
Day	-21 to -7	0	14	28	29	
Informed Consent	X					
Inclusion/Exclusion	X	X				
Demographics (sex, age, race and ethnicity)	X					
Medical and Social History (including tobacco, alcohol, caffeine and drug use)	X					
Prior/Concomitant Medications	X	X	X	X	X	X
Physical Examination	X				X	X
12-lead ECG	X					
Height, Weight, BMI	X	X	X	X		X
Vital Signs	X	X	X	X	X	X
Chemistry, Hematology, Urinalysis	X				X 	X
Blood Collection for Plasma Glucose, Metabolites and Hormones	X			X	X	
Urine Drug Screen	X					
Serum Pregnancy Test	X					
Urine Pregnancy Test				X		
Breathalyzer	X	X	X	X	X	

	Screening	Treatment Period			Discharge / End of Study	Early Withdrawal
				TRACER Infusion		
Visit	0	1	2		3	
Week	-3 to -1	0	2		4	
Day	-21 to -7	0	14	28	29	
HbA1c	X	X	X	X	X	
Randomization		X				
Dispense study medication		X	X			
Collect study medication and review for compliance			X	X		
CRU Admission				X		
In-Clinic Dosing				X		
TRACER Infusion				X	X	
Blood Collection for Tracer Marked Glucose, Metabolites and Hormones				X	X	
Standard Meals				X	X	
CRU Discharge					X 	X
Adverse Events		X	X	X	X	X
End of Study					X	X

 Weight will be measured at each visit. Height will be measured and BMI will be calculated at Screening.

 Blood draw will be performed after the 16-hour infusion is complete.

 A blood plasma sample will be collected at Screening and during infusion for assessment of plasma glucose, metabolites and hormones according to [Table 2](#).

 Serum pregnancy test and urine pregnancy test will be performed for women of childbearing potential (WCBP) only.

 Subjects will be started on a 16-hour infusion of TRACER immediately following dosing. Refer to [Appendix A](#) (Guidelines for TRACER Infusion).

 Blood samples will be collected during the duration of infusion based on the blood draw schedule in [Table 2](#).

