**Table 2: Blood Draw Schedule**

additive	EDTA+NaF	EDTA	EDTA	EDTA+30 µL diprotin+20 µL Foy°	EDTA+30 µL diprotin+20 µL Foy°	
assay	Tracer	Glucose	Metabolites#	Hormones§	Backup	total
Time	mL	mL	mL	mL	mL	mL
Baseline*	2	1	3	3	4	13
45 min	2	1	3	3		9
90 min	2	1	3	3		9
120 min	2	1	3	3		9
150 min	2	1	3	3		9
3 hours	2	1	3	3		9
4 hours	2	1	3	3		9
5 hours	2	1	3	3		9
6 hours	2	1	3	3		9
7 hours	2	1	3	3		9
8 hours	2	1	3	3		9
9 hours	2	1	3	3		9
10 hours	2	1	3	3		9
11 hours	2	1	3	3		9
12 hours	2	1	3	3		9
13 hours	2	1	3	3		9
14 hours	2	1	3	3		9
15 hours	2	1	3	3		9
16 hours	2	1	3	3	4	13
Total	38	19	57	57	8	179

\* before starting tracer infusion

° Foy master solution = 0.035 mg in 10 mL of saline

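### During home dosing no glucose measurement is scheduled, so the > 300 mg/dL rule can act only on unscheduled readings; a fasting glucose read on site at Visit 2 would about halve the gap

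*Combined protocol and SAP*

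**What the plan says.** Section 7.4.4 sets the limit at 300 mg/dL whether or not the subject has symptoms. The first step is "Subjects who have a blood glucose reading > 300 mg/dL will have the reading repeated 1-2 hours later". If the value stays above the limit, or symptoms of hyperglycemia persist, "the subject will be instructed to contact the investigative site for follow-up". The same section says that hyperglycemia is in general not an adverse event in this population, but it foresees cases caused by worsening disease or an ineffective study drug.

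The schedule for glucose is as follows.

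- **Section 6.2.3:** "Plasma glucose levels will be collected prior to dosing and after 28 days of dosing".
- **Table 1, footnote 3:** "A blood plasma sample will be collected at Screening and during infusion for assessment of plasma glucose, metabolites and hormones".
- **Table 2:** the first infusion-day sample is drawn "before starting tracer infusion", at about 8 PM on Day 28.
- **Safety chemistry and urinalysis** (both include glucose, Section 6.1.5.1): Screening, Day 29 after the infusion, and the early-withdrawal visit (Section 3.6: "Collection of fasted blood and urine samples for clinical safety labs for hematology, serum chemistry and urinalysis").
- **Visit 2 (Section 3.3.2):** "Subjects will report to the clinic in morning following a 10-hour fast", and the only blood test listed is "Blood sample will be collected to measure HbA1c".

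The draws at Visit 1 and on the morning of Day 28 are also for HbA1c only (Sections 3.3.1 and 3.4.1).

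**The concern.** A rule that applies without symptoms works only where glucose is measured. The last step of Section 7.4.4, contacting the site, suggests readings taken away from the clinic. Yet the protocol does not supply a meter, ask for self-monitoring or provide a glucose log. HbA1c at Visit 2 cannot be compared with a limit written in mg/dL of blood glucose.

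Subjects enter with HbA1c between 7.5% and 11%, and one arm takes placebo. At stake is whether a marked fasting hyperglycemia without symptoms is noticed while the subject is still dosing at home. A scheduled value would also inform the investigator, because Section 5.6 allows otherwise prohibited antidiabetic drugs for rescue.

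**Working it through.** **1. The plan's own figure.** Table 2 lists 19 time points, each with 2 + 1 + 3 + 3 = 9 mL, plus two backup tubes of 4 mL: 19 × 9 + 2 × 4 = 171 + 8 = 179 mL. This matches the stated total. Each glucose sample takes 1 mL, and there are 19 per subject (1 before the infusion, 18 after it starts).

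**2. Scheduled glucose by visit, for a subject who stays in the study** (Table 1 and the visit lists)

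| Time | Blood drawn | Glucose scheduled? |
|---|---|---|
| Screening, Day -21 to -7 | Chemistry, plasma glucose, HbA1c | Yes |
| Visit 1, Day 0 | HbA1c | No |
| Visit 2, Day 14 | HbA1c | No |
| Day 28, morning | HbA1c | No |
| Day 28, about 8 PM, to Day 29 | Table 2 samples, then chemistry | Yes, 19 plus chemistry |

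The count between the first dose and the evening of Day 28 is 0.

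**3. Length of the on-treatment stretch now.** Day 0 to Day 28 is 28 days. Home doses: 1 or 2 on Day 0, then 27 × 2 = 54 on Days 1 to 27, so 55 to 56 before the in-clinic dose on the morning of Day 28.

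Counted from Screening, the gap is 28 + 7 = 35 to 28 + 21 = 49 days. Of that, 7 to 21 days fall before any study drug is taken, so 28 days is the relevant figure.

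**4. With a glucose at Visit 2.** The protocol says only that Visit 2 is in the morning; 8 AM is assumed here.

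- Day 0 to Day 14: about 14 days.
- Day 14, 8 AM, to Day 28, 8 PM: 14 + 12/24 = 14.5 days.

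The longest stretch therefore falls from 28 to about 14.5 days. Scheduled values before the infusion day rise from 0 to 1 per subject, or about 40 in all.

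**5. Added blood.** 1/179 = 0.6% of the Table 2 volume.

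**6. Yield.** The documents give no rate of fasting glucose above 300 mg/dL. Purely as an assumption, rates of 1%, 5% and 10% at Visit 2 would mean 40 × 0.01 = 0.4, 40 × 0.05 = 2 and 40 × 0.10 = 4 subjects found. Nothing in the protocol anchors these rates, and the true yield could be zero.

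**The case against.** The strongest reply is that one tube does not repair the rule. A single fasting value on Day 14 leaves every other day, and every post-meal value, dependent on unscheduled readings. That stands: the gap is narrowed and not closed.

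A second reply concerns timing. Section 7.4.4 wants a repeat within 1 to 2 hours, but Section 6.1.5 promises no turnaround, and Section 9.1.1 has laboratory results sent to the contract research organization for import into the database. A result that arrives after the subject has left cannot trigger that repeat. This also stands, and it is why the value has to be read on site the same morning.

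Third, the protocol's silence about meters does not show that subjects do not self-test. All have had diagnosed type 2 diabetes for at least 6 months, and persistent symptoms separately trigger contact with the site. This stands too: what can be said is that home readings are unscheduled, not that they do not occur.

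Fourth, Section 5.6 gives no glucose threshold for rescue, so a high value leads to follow-up by the investigator and to no fixed action. That is true, and the proposal does not change it.

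A reader might infer that glucose goes unmonitored throughout the trial. The documents do not support this: glucose is measured at Screening, 19 times on Days 28 to 29, and in the chemistry of anyone who withdraws early. The gap is confined to home dosing.

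**Conclusion.** The point holds as a minor one. For a subject who stays in the study, Section 7.4.4 has no scheduled input from Day 0 to the evening of Day 28, and one added measurement about halves that stretch. The finding rests on the count of scheduled samples, which is firm. The 14.5-day figure rests on an assumed 8 AM visit. The clinical gain cannot be sized from the documents.

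A reader might also infer a threat to the efficacy results or a bias between arms. Nothing supports either: the added value enters no primary or secondary endpoint, the missing measurement applies equally to both arms, and the case for change is patient safety alone.

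**What to change.** Add a fasting glucose to Visit 2 in Section 3.3.2 and Table 1, taken from the existing HbA1c draw (1 mL) and read on site the same morning. If it is above 300 mg/dL, repeat it 1 to 2 hours later, before the subject leaves. If it remains above 300 mg/dL, the investigator follows up at that visit, since telling a subject who is already in the clinic to contact the site would serve no purpose.

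The cost is at most about 40 first readings, a few repeats, and an occasional Visit 2 that runs 1 to 2 hours longer. No new visit, fast or venepuncture is needed for the first reading; a repeat needs a second sample. The change assumes that the site can measure glucose on the spot, which the protocol does not state and the sponsor should confirm.
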